##### **3.3.1. Adverse Events**

An adverse event is considered treatment emergent (TEAE) relative to a given treatment if the event occurs during the on-treatment period (regardless if it was seen prior to the start of treatment). An adverse event is considered treatment-related as assigned by the investigator.

Adverse events (AEs) will be coded to preferred term (PT) and system organ class (SOC) using the Medical Dictionary for Regulatory Activities (MedDRA) and classified by severity using the National Cancer Institutes (NCI) Common Terminology Criteria for Adverse Events (CTCAE), version 4.03. Adverse events occurring on the same day as the first dose of study treatment will be considered to have occurred during the on-treatment period. All other assessments which occur on the same day as the first dose of study treatment will be considered as baseline assessments.

Safety data collected outside the on-treatment period as described above will be listed but not summarized.

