10.3.1. Definition of AE

AE Definition

• An AE is any untoward medical occurrence in a patient or clinical study participant, temporally associated with the use of study intervention, whether or not considered related to the study intervention.• NOTE: An AE can therefore be any unfavorable and unintended sign (including an abnormal laboratory finding), symptom, or disease (new or exacerbated) temporally associated with the use of study intervention.

Events Meeting the AE Definition

• Any abnormal laboratory test results (hematology, clinical chemistry, or urinalysis) or other safety assessments (eg, ECG, radiological scans, vital sign measurements), including those that worsen from baseline, considered clinically significant in the medical and scientific judgment of the investigator. Any abnormal laboratory test results that meet any of the conditions below must be recorded as an AE:
• Is associated with accompanying symptoms.• Requires additional diagnostic testing or medical/surgical intervention.• Leads to a change in study dosing (outside of any protocol-specified dose adjustments) or discontinuation from the study, significant additional concomitant drug treatment, or other therapy.• Exacerbation of a chronic or intermittent preexisting condition including either an increase in frequency and/or intensity of the condition.• New conditions detected or diagnosed after study intervention administration even though it may have been present before the start of the study.• Signs, symptoms, or the clinical sequelae of a suspected drug-drug interaction.• Signs, symptoms, or the clinical sequelae of a suspected overdose of either study intervention or a concomitant medication. Overdose per se will not be reported as an AE/SAE unless it is an intentional overdose taken with possible suicidal/self-harming intent. Such overdoses should be reported regardless of sequelae.• The signs, symptoms, and/or clinical sequelae resulting from lack of efficacy will be reported as an AE or SAE if they fulfill the definition of an AE or SAE and meet the requirements as per Section 8.3.8.1. Also, “lack of efficacy” or “failure of expected pharmacological action” does not constitute an AE or SAE.

Events NOT Meeting the AE Definition

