- If a participant dies during participation in the study or during a recognized follow-up period, the investigator will provide Pfizer Safety with a copy of any postmortem findings including histopathology.
- New or updated information will be recorded in the originally completed CRF.
- The investigator will submit any updated SAE data to the sponsor within 24 hours of receipt of the information.

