#### **3.2. Baseline Variables**

The date of first dose (start date) of study treatment is the earliest date of non-zero dosing of any study drug. The date of last dose of study treatment is the latest date of non-zero dosing of any study drug.

No windowing will be applied when defining baseline. Any deviations from the protocol specified window will be documented as protocol deviations.

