#### **3.3. Safety Endpoints**

Safety endpoints will be summarized based on the on-treatment period unless otherwise specified.

On-treatment is defined as the time from the first non-zero dose of study treatment to the last non-zero dose + 28 days.

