## **6. ANALYSES AND SUMMARIES**

Analyses for B1371019 and B1371012 will be conducted separately and independently.

All participants who receive any study treatment (safety analysis set) will be included in the summaries and listings of safety data. Overall safety profile and tolerability of azacitidine or glasdegib + azacitidine will be characterized by type, frequency, severity, seriousness, timing, and relationship to study therapy of AEs.

AEs will be classified using the MedDRA classification system. The severity of the toxicities will be graded according to the NCI CTCAE version 4.03.

In all summaries, emphasis will be placed on TEAEs (events occurring from Amendment 6 consent up to last dose + 28 days). AEs will be summarized by the frequency of participants experiencing TEAEs corresponding to body systems and MedDRA preferred term and by worst NCI CTCAE (version 4.03) grade.

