### **6.3.1. Adverse Events**

All analyses will be based on treatment emergent events unless otherwise specified. Treatment emergent is defined in [Section 3.3.1](#).

Seriousness, toxicity grade, study drug action taken (interruption, reduction, and withdraw) are as reported by the investigator on the adverse event CRF.

Summaries by treatment arm, SOC and PT in decreasing frequency based on the frequencies observed in the glasdegib arm will be provided for:

- Treatment Emergent Events by Maximum Toxicity Grade (All Causality);
- Treatment Emergent Events by Maximum Toxicity Grade (Treatment Related); Serious Treatment Emergent Events by Maximum Toxicity Grade (All Causality);
- Serious Treatment Emergent Events by Maximum Toxicity Grade (Treatment Related).

An event will be considered treatment related if the investigator considered the event related to the study drug or this information is unknown.

- Treatment Emergent Adverse Events Leading to Dose Interruptions by Maximum Toxicity Grade (All Causality) separately for each study drug, for chemotherapy, and for any study treatment;
- Treatment Emergent Adverse Events Leading to Dose Reductions by Maximum Toxicity Grade (All Causality) separately for each study drug, for chemotherapy, and for any study treatment;
- Treatment Emergent Adverse Events Leading to Permanent Withdrawal by Maximum Toxicity Grade (All Causality) separately for each study drug, for chemotherapy, and for any study treatment;
- Serious Treatment Emergent Events (All Causality).

Each patient will be counted only once within each PT.

As described in [Section 5.3.2](#), in case a patient has events with missing and non-missing toxicity grades, the maximum of the non-missing grade will be displayed. Missing grade will only be displayed in the event that only one event has been reported for a patient and the grade is missing.

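### The TEAE rule has no worsening criterion and no single window start, so an AE open at Amendment 6 entry that worsens can be missed in the TEAE tables, or unchanged carry-over toxicity counted

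*SAP*

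**What the plan says.** The definition in SAP 3.3.1 turns on whether the AE falls in a window: "if the event occurs during the on-treatment period (regardless if it was seen prior to the start of treatment". It does not say whether occurring means starting or being present, and it makes no grade comparison.

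The window itself is given in two ways:
- SAP 3.3: "On-treatment is defined as the time from the first non-zero dose of study treatment to the last non-zero dose + 28 days". SAP 3.2 adds: "The date of first dose (start date) of study treatment is the earliest date of non-zero dosing of any study drug". Neither sentence mentions Amendment 6.
- SAP 6: "emphasis will be placed on TEAEs (events occurring from Amendment 6 consent up to last dose + 28 days". Protocol 9.4.1 gives the same window. Neither has a worsening test.

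The classification decides what is tabulated. SAP 6.3.1 states "All analyses will be based on treatment emergent events unless otherwise specified" and points back to 3.3.1 for the definition. SAP 3.3.1 adds: "Safety data collected outside the on-treatment period as described above will be listed but not summarized".

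On recording, protocol 10.3.1 includes among events that meet the AE definition: "Exacerbation of a chronic or intermittent preexisting condition including either an increase in frequency and/or intensity of the condition". Protocol 10.3.3, under follow-up of AEs and SAEs, says: "New or updated information will be recorded in the originally completed CRF". Neither section says whether a grade increase in an AE that is already open gets its own record and onset date.

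**The concern.** Amendment 6 is a continuation phase. Its inclusion criteria require ongoing benefit from study treatment, so everyone is exposed before the new observation period begins and some may enter with toxicities still open. In that setting, worsening of an existing toxicity is one of the more informative safety signals. Unchanged toxicity from the earlier phase is not new information.

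AEs and SAEs are the only endpoint (protocol 3, SAP 2.1). A rule that can leave out the worsening, or count the unchanged event, therefore affects the main output of this phase and the disclosure tables in SAP 6.3.1.1. Which error occurs, if either, would depend on programming choices and site habits that the plan does not settle.

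**Working it through.** The documents state no sample size, power or alpha for Amendment 6, so there is no figure to reproduce. The check is to apply the rule to simple event histories.

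**Illustrative timeline (assumed).** First-ever dose on day −300, Amendment 6 consent on day 0, first Amendment 6 dose on day 1, last dose on day 200. The window ends on day 200 + 28 = 228. A Grade 1 AE starts on day −60, during earlier study treatment.

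**Histories.**
- (a) The AE stays at Grade 1.
- (b) It becomes Grade 4 on day 50, and the site updates the same record, so the onset date stays at day −60.
- (c) It becomes Grade 4 on day 50, and the site opens a new record with onset on day 50.

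**Tests.** Under the onset reading, an AE counts if window start ≤ onset ≤ 228. Under the presence reading, it counts if it is ongoing at any time in the window.

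| Window start | Reading | (a) unchanged | (b) same record | (c) new record |
|---|---|---|---|---|
| First-ever dose (SAP 3.2 and 3.3 taken literally) | onset or presence | counted, Grade 1 | counted, Grade 4 | counted, Grade 4 |
| Amendment 6 consent or first Amendment 6 dose | onset | not counted | **listed only** | counted, Grade 4 |
| Amendment 6 consent or first Amendment 6 dose | presence | counted, Grade 1 | counted, Grade 4 | counted, Grade 4 |

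In row 2, (b) fails because −60 is before 0 (or 1), while (c) passes because 50 lies between the start and 228. In row 1, −60 is after −300, so all three histories count.

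**What follows.**
- The Grade 4 worsening is lost from the TEAE tables only when three things coincide: an Amendment 6 start, the onset reading and same-record updating.
- Unchanged carry-over is counted under a first-ever-dose start or the presence reading.
- An Amendment 6 start, the onset reading and a new record for the worsening give neither error. The documents do not prescribe this combination.

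**Weight of one participant.** The maxima are 34 from B1371019 and 3 from B1371012 (SAP 2.2). The split by arm is not given, so an equal split of 17 and 17 is assumed.
- 1/34 = 2.9%
- 1/17 = 5.9%
- 1/3 = 33.3%

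SAP 6.3.1.1 tabulates non-serious TEAEs above 5% in either arm. Since 1/19 = 5.3% and 1/20 = 5.0%, one participant is enough to cross that threshold in any arm of 19 or fewer.

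**The case against.** The strongest objection is that the plan may already answer the question elsewhere. SAP 5.3 refers the treatment-emergent algorithm to the CDISC Safety Rulebook, which may contain a worsening rule. This stands in part: the documents do not show that no rule exists, only that none is written in them. But the reference sits in the missing-data section and gives no version or content, and SAP 6.3.1 names 3.3.1 as the definition.

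Second, the SAP leans towards onset. SAP 5.3.1 decides emergence from start dates, and SAP 5.2.2 refers to AE onset when computing study day. This makes the presence reading less likely. It also supplies one of the three conditions for losing a worsening.

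Third, protocol 10.3.1 treats an exacerbation as an AE, and the SAP's date-imputation rules foresee series of similar events. If the worsening is entered as a new AE, it is captured. The sentence in 10.3.3 about updating the CRF does not mention grades or onset dates. All this is fair, but it leaves the result to site practice or to CRF guidance that is not part of these documents.

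A reader might also infer more than the documents support:
- *The event vanishes from every table.* It does not. AE-driven dose reductions and interruptions (SAP 6.2.3.6) come from the dosing CRF, and discontinuations due to AEs (SAP 6.2.2.1) are not defined through TEAE status. The fatal-event summary in SAP 6.3.1.1 lacks the treatment-emergent label that its neighbours carry, so a fatal worsening may still appear there. The event is listed in any case, and SAEs must still reach the sponsor within 24 hours (protocol 8.3.1.1).
- *The loss occurs under any window start.* It does not: with a first-ever-dose start, an event that began on earlier study treatment is inside the window.
- *Open toxicities at entry are the norm.* The documents give no such figure.

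**Conclusion.** The concern holds as an ambiguity in the written rule. The text has no worsening criterion and two conflicting window starts. Permitted readings give opposite errors: a worsened AE omitted from the TEAE tables, or unchanged carry-over counted as emergent. How many participants would be affected cannot be estimated, because the documents give neither the number entering with open AEs nor how often such AEs worsen. The percentages above show only how much one misclassified participant weighs, and the 5.9% rests on the assumed equal split.

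This should be corrected before analysis, but it does not undermine the study. The phase is descriptive, has at most 34 + 3 = 37 participants and tests no hypothesis. Expedited safety reporting is unaffected.

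**What to change.** 1. **One window start.** In SAP 3.3, tie the start to Amendment 6 and reconcile it with SAP 6 and protocol 9.4.1. Those two already use consent, so adopting consent needs the fewest edits. Make the first-dose wording in SAP 3.2 consistent with the choice.
2. **Onset or worsening.** In SAP 3.3.1, define a TEAE as an AE with onset on or after that start, or an AE open at that start whose CTCAE grade or seriousness increases within the window. Count the latter at the worsened grade. The reference grade can come from the Amendment 6 screening visit, where the schedule of activities already has AE monitoring.
3. **Unchanged carry-over.** List these AEs separately as ongoing at entry and leave them out of the TEAE counts.
4. **Recording.** State in the CRF guidance, in line with protocol 10.3.3, that worsening of an AE open at entry is entered as a new record dated at the worsening.
5. **Rulebook.** Say in SAP 5.3 that the definition in 3.3.1 prevails if the rulebook differs.

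Under this rule, history (a) is not a TEAE, and (b) and (c) are both TEAEs at Grade 4, however the site records the event. The cost is a few sentences and a small added data-entry step, with no new assessments.

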##### **3.3.2. Laboratory Data**

Not applicable.

## 4. ANALYSIS SETS

The B1371019 and B1371012 participants will be analyzed separately and independently. Analysis sets and the applicable analysis using the analysis set is summarized in the table below.

Analysis Set	Population	Applicable Analysis (for additional information see Section 6 )
Safety Analysis (SA) Set	All participants who received at least one dose of study after consenting to participate in Protocol Amendment 6	Safety analysis for B1371019 Safety analysis for B1371012

## 5. GENERAL METHODOLOGY AND CONVENTIONS

### 5.1. Hypotheses and Decision Rules

Not applicable.

### 5.2. General Methods

For study B1371019, demographic data will be summarized by treatment arm and for both treatment arms combined. Disposition, exposure, and safety data will be summarized by treatment arm only. For study B1371012, summary will be provided for all participants continuing to Protocol Amendment 6.

The safety analyses of participants from Study B1371019 and participants originating from Parent Study B1371012 will be conducted separately and independently of each other.

#### 5.2.1. Pooling of Data by Center

Not applicable.

#### 5.2.2. Definition of Study Day

Start day of study treatment is the day of the first non-zero dose of any study treatment.

The study day for assessments occurring on or after the start day of study treatment (eg, adverse event onset, laboratory date) will be calculated as:

Study day = Date of the assessment/event - start date of study treatment + 1.

The study day for assessments occurring prior to the start day of study treatment (eg, baseline characteristics, medical history) will be negative and calculated as:

Study day = Date of the assessment/event –start date of study treatment.

The study day will be displayed in all relevant data listings.

### **5.2.3. Definition of Cycle and Cycle Day**

Cycle start and end dates are derived per patient and not per study treatment.

- For Cycle X, the actual cycle start date for each subject is the earliest start date of dosing (dose>0 at that visit) in Cycle X visit CRF exposure page.
- For all but the last cycle.
  - Actual cycle end date is calculated as the start date of the next cycle minus one day.
  - Actual cycle duration is calculated from Day 1 of a cycle to the day prior to Day 1 of the next cycle, as follows:

$$\text{Actual Cycle Duration} = \text{cycle end date} - \text{cycle start date} + 1.$$

- For the last cycle, actual cycle duration is calculated as follows:
  - Actual Cycle Duration = last date of non-zero study treatment – cycle start date + 1.

The cycle day will be calculated as:

$$\text{Cycle day} = \text{Date of the assessment/event} - \text{cycle start date} + 1.$$

### **5.2.4. Date of Last Contact**

Not applicable.

### **5.2.5. Disease Assessment Date**

Not applicable.

### **5.2.6. Unscheduled Assessments**

Not Applicable.

### **5.2.7. Standard Derivations and Reporting Conventions**

The following conversion factors will be used to convert days into weeks, months or years:  
1 week = 7 days, 1 month = 30.4375 days, 1 year = 365.25 days.

Percentages will be reported to one decimal place. The rounding will be performed to closest integer/first decimal using the common mid-point between the two consecutive values, eg, 5.1 to 5.4 will be rounded to an integer of 5, and 5.5 to 5.9 will be rounded to an integer of 6.

### **5.2.8. Analyses for Continuous Data**

Continuous variables will be summarized using descriptive statistics ie, number of non-missing values and number of missing values [ie, n (missing)], mean, median, standard deviation (SD), minimum, maximum and first and third quartile (Q1 and Q3).

In case the analysis refers only to certain visits, estimates will be based on the number of patients with an assessment at that visit, unless otherwise specified.

### **5.2.9. Analyses for Categorical Data**

Qualitative variables will be summarized by frequency counts and percentages. Unless otherwise specified, the calculation of proportions will include the missing category. Therefore counts of missing observations will be included in the denominator and presented as a separate category.

In case the analysis refers only to certain visits, percentages will be based on the number of patients with an assessment at that visit, unless otherwise specified.

### **5.2.10. Analyses for Time to Event Data**

Not applicable.

## **5.3. Methods to Manage Missing Data**

Unless otherwise specified, all data will be evaluated as observed, and no imputation method for missing values will be used.

Any imputations will occur at the analysis dataset level. Additionally, in all patient data listings imputed values will be presented and flagged as imputed.

Missing statistics, eg, when they cannot be calculated, should be presented as 'ND' for not done, 'NR' for not reached or 'NA' for not applicable. For example, if N=1, the measure of variability cannot be computed and should be presented as 'ND' or 'NA'.

CDISC Safety Rulebook will be followed when handling the missing/partial dates, treatment emergent AE algorithm, missing AE grades, etc.

### **5.3.1. Missing Dates**

For purposes of data listings, dates will reflect only the information provided by the investigator on the CRF.

If start dates for adverse events are completely missing a worst case approach will be taken whereby the events will be considered treatment emergent. If only partial information are available (eg, only a month and year or only a year) and the partial information provide sufficient information to indicate the dates are prior to the start of study treatment (eg, month/year less than month/year of first dose) then these will be considered to have started prior to treatment; otherwise a similar worst case approach will apply and these will be considered to have started after treatment.

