8.3.1. Time Period and Frequency for Collecting AE and SAE Information

The time period for actively eliciting and collecting AEs and SAEs (“active collection period”) for each participant begins from the time the participant provides informed consent, which is obtained before the participant’s participation in the study (ie, before undergoing any study-related procedure and/or receiving study intervention), through and including a minimum of 28 calendar days after the last administration of the study intervention.

Follow-up by the investigator continues throughout and after the active collection period and until the AE or SAE or its sequelae resolve or stabilize at a level acceptable to the investigator and Pfizer concurs with that assessment.

For participants who are screen failures, the active collection period ends when screen failure status is determined.

If the participant withdraws from the study and also withdraws consent for the collection of future information, the active collection period ends when consent is withdrawn.

If a participant definitively discontinues or temporarily discontinues study intervention because of an AE or SAE, the AE or SAE must be recorded on the CRF and the SAE reported using the CT SAE Report Form.

Investigators are not obligated to actively seek AEs or SAEs after the participant has concluded study participation. However, if the investigator learns of any SAE, including a death, at any time after a participant has completed the study, and he/she considers the event to be reasonably related to the study intervention, the investigator must promptly report the SAE to Pfizer using the CT SAE Report Form.

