9.4.1. Safety Endpoint(s)

All participants who receive any study treatment (safety analysis set) will be included in the summaries and listings of safety data. Overall safety profile and tolerability of azacitidine or glasdegib + azacitidine will be characterized by type, frequency, severity, seriousness, timing, and relationship to study therapy of AEs.

AEs will be classified using the MedDRA classification system. The severity of the toxicities will be graded according to the NCI CTCAE version 4.03.

In all summaries, emphasis will be placed on TEAEs (events occurring from Amendment 6 consent up to last dose + 28 days). AEs will be summarized by the frequency of participants experiencing TEAEs corresponding to body systems and MedDRA preferred term and by worst NCI CTCAE (version 4.03) grade.

AEs leading to permanent discontinuation of any study treatment, and SAEs will be considered with special attention. AE reporting, including SUSARs, will be carried out in accordance with applicable local regulations. Reasons for discontinuation from study treatment will be summarized by the frequency of participants with each reason described.

Descriptive statistics ie, number of non-missing values and number of missing values (ie, n [missing]), mean, median, SD, minimum, maximum and first and third quartile (Q1 and Q3) for treatment duration ([last dose date - first dose date after Amendment 6 consent +1]/7) will be provided.

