### **AE Onset Date:**

The following imputation rules apply if the event is unique for a patient or it is the first of a series of similar events; otherwise, the AE Onset Date will not be imputed:

- If the AE Collection Date is not missing, is less than the Date of First Exposure to Treatment, and is less than the AE Stop Date, then AE Onset Date is set to the Date of AE Collection.
- If the Previous Visit Date is greater than the Date of First Exposure to Treatment and less than the AE Stop Date, the AE Start Date is set to the previous visit date.

- If the Date of First Exposure to Treatment is greater than the previous visit date and less than the AE Stop Date, the AE Onset Date is set to the Date of First Exposure to Treatment.
- Otherwise AE Onset Date is set to the AE Stop Date.

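### SAP 5.3.1 sets treatment-emergent status for AEs with missing or partial start dates without checking the stop date, and does not say which of its competing date rules prevails

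*SAP*

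**What the plan says.** SAP 5.3.1 (Missing Dates) has two branches for AE start dates.

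- Completely missing: "If start dates for adverse events are completely missing a worst case approach will be taken whereby the events will be considered treatment emergent".
- Partial: the event is pre-treatment if the known month or year is clearly before first dose; "otherwise a similar worst case approach will apply and these will be considered to have started after treatment".

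Neither branch mentions the AE stop date or last dose + 28 days.

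Three other provisions bear on the same records:

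- **AE Onset Date**, also within 5.3.1, imputes an onset, but with limited scope: "The following imputation rules apply if the event is unique for a patient or it is the first of a series of similar events". Events are similar if they share a verbatim term. Every conditional step compares a date with the AE stop date, and the default reads: "Otherwise AE Onset Date is set to the AE Stop Date".
- **Other Missing or Partial Dates**, also within 5.3.1, replaces a missing day with the first of the month, and a missing day and month with 1 January.
- **SAP 5.3** says the CDISC Safety Rulebook will be followed for missing and partial dates and for the treatment-emergent algorithm. Its content is not given.

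The window these rules serve is defined in SAP 3.3: "On-treatment is defined as the time from the first non-zero dose of study treatment to the last non-zero dose + 28 days". SAP 3.3.1 adds: "Safety data collected outside the on-treatment period as described above will be listed but not summarized". SAP 6 and Protocol 9.4.1 open the window earlier: "events occurring from Amendment 6 consent up to last dose + 28 days".

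**The concern.** A worst-case rule should settle uncertainty. If the start date is missing but the recorded stop date precedes the window, nothing is uncertain: the event began and ended outside it. Read literally, SAP 5.3.1 overrides that information and moves the event from the listings into the summaries.

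All AEs and SAEs are the only endpoint (Protocol 3, SAP 2.1). A misclassified event would enter the treatment-emergent tables by maximum grade and, where serious, the serious-event tables (SAP 6.3.1). Because several rules address the same records with no order among them, two programmers could also produce different tables from the same data.

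**Working it through.** There is no stated figure to reproduce: hypotheses and sample size are marked not applicable. The check applies each rule to constructed records.

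**1. Records with no start date.** Assumed days: Amendment 6 consent −5, first dose 0, last dose 100, so the window ends at 100 + 28 = 128. First dose is taken as the first after Amendment 6 consent, as Protocol 9.4.1 does for treatment duration; SAP 3.3 does not say this. The AE collection date is day 3 for the first two records and the stop day for the others, so the collection-date step never applies.

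| Stop day | Previous visit | Main 5.3.1 rule | Onset under AE Onset Date | In SAP 3.3 window? | In SAP 6 window? |
|---|---|---|---|---|---|
| −2 | −5 | TEAE | −2 (default) | No | Yes |
| −20 | −30 | TEAE | −20 (default) | No | No |
| 50 | 28 | TEAE | 28 (previous visit) | Yes | Yes |
| 140 | 112 | TEAE | 112 (previous visit) | Yes | Yes |
| 150 | 135 | TEAE | 135 (previous visit) | No | No |

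- *Stop day −20.* The event certainly lies outside both windows, yet the main rule counts it.
- *Stop day −2.* It is outside the SAP 3.3 window but may be inside the SAP 6 window, so the answer depends on which window start applies.
- *Stop day 150.* The true onset could lie inside the window, so the main rule's worst case is legitimate here. It is the imputed onset that would drop the event. Giving the AE Onset Date rules priority is therefore not the remedy.

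The pre-dose result is general. If the stop date is before first exposure, the second step needs a previous visit after first exposure but before the stop date, and the third needs first exposure before the stop date. Both are impossible. Onset is then a pre-exposure collection date or the stop date itself.

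**2. Repeat events.** If either of the first two records is a later event in a series, AE Onset Date imputes nothing. The main rule stands alone and counts it.

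**3. Partial date.** Take a start recorded only as 2021, a stop date of 20 January 2021 and a first dose in 2021. Amendment 6 is dated 02 February 2021, so no Amendment 6 window can open before then and the event is outside it.

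- Main rule: 2021 is not earlier than the year of first dose, so the event is counted.
- Other Missing or Partial Dates, if it covers AE dates: start is 1 January 2021, so it is not counted.

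If the same event had no stop date, its timing would be truly uncertain. The 1 January rule would still exclude it, which is the wrong direction for a worst-case approach.

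**4. Weight of one participant.** The increment is 100/n percentage points, for a participant who does not otherwise have that preferred term.

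- B1371012, n at most 3: 100/3 = 33.3.
- B1371019, two arms sharing at most 34, so the smaller has at most 34/2 = 17: 100/17 = 5.9.
- The disclosure cut of more than 5% for non-serious events (SAP 6.3.1.1) is passed by one participant when n is 19 or fewer (100/19 = 5.3) but not at 20 (100/20 = 5.0).

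**The case against.** The strongest reply is that the main rule should not be read alone. The AE Onset Date rules sit in the same section, use the stop date throughout, and give unique or first-of-series events a pre-dose onset whenever the stop date is pre-dose. The rulebook may settle the rest. This stands in part: a reader might infer that the SAP ignores the stop date altogether, and it does not. For those events the defect is an unresolved conflict. Repeat events remain uncovered, and nothing says which rule decides.

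A reader might also infer that events starting after the window are counted. The documents do not establish that. The wording for partial dates can be read as fixing only the lower bound, with the 28-day limit still applying. Protocol 8.3.1 does require a report "if the investigator learns of any SAE, including a death, at any time after a participant has completed the study" if the event is considered reasonably related, but on the CT SAE Report Form; Protocol 8.3.1.2 requires CRF recording only within the active collection period. That period runs for a minimum of 28 days, so a few late records are possible. The text is ambiguous here, not wrong.

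It is also fair to say that the output is descriptive, that any error from the main rule over-reports, and that one participant exceeds 5% in any small arm whatever the rule. These points limit the consequence without making the classification correct.

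**Conclusion.** The point holds in a limited form. The main rule in SAP 5.3.1 can count an AE whose recorded stop date precedes the window. This is a plain error for repeat events. It is a conflict with AE Onset Date for unique or first-of-series events, and can be one with Other Missing or Partial Dates for partial dates.

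The frequency cannot be determined. A reader might suppose that a large store of AEs from the earlier treatment phase would flood the tables. But SAP 2 confines the analysis to safety data collected under Amendment 6, and neither document says that earlier records are loaded. Events resolving between consent and first dose are collected in any case (Protocol 8.3.1). No rate of missing start dates is given, and the number is probably small.

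The size per affected participant is at least 33 percentage points in the B1371012 group and at least 5.9 in the smaller B1371019 arm. Both assume the stated maximum enrolment and a participant without another event of that preferred term; fewer participants would make the increments larger. This is worth correcting because it concerns the only endpoint and the correction is cheap.

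**What to change.** Amend SAP 5.3.1 as follows:

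1. An AE with a missing or partial start date is treatment emergent unless (a) its recorded stop date, full or partial, is before the start of the TEAE window, or (b) the known part of its start date lies wholly before the window or wholly after last dose + 28 days.
2. For treatment-emergent status, this rule takes precedence over AE Onset Date, Other Missing or Partial Dates and the CDISC Safety Rulebook.
3. Use one window start throughout. SAP 3.3 uses first dose; SAP 6 and Protocol 9.4.1 use Amendment 6 consent. If first dose is kept, say that it means the first dose after that consent.

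Condition (a) should use the stop date as reported, not an imputed one. The worst-case rule remains for every record these conditions do not settle. The cost is a few sentences in the SAP, alignment of the window definition, and two conditions in the AE derivation program. No new data are needed.
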